### 6.3 Assessment of secondary endpoint/outcome(s)

Morbidity definitions are shown in Appendix 11, then applied to the Clavien Dindo score and CCI score (see Appendix 11 'Definitions of Outcomes' and Appendix 14 'How to calculate the CCI Score').

#### 6.4 Other comments on endpoints:

The following data will be extracted from clinical charts: age, gender, weight, height, variables for CCI, variables for SORT calculation (see Appendix 12 'Surgical Outcome Risk Tool (SORT)'),

ASA classification, relevant medical history, preoperative diabetes medication (substance classes only), type of anesthesia, date, type, and location of surgery, procedure duration, type and date if ICU admission, date of discharge from ICU and from hospital. For details, please see the eCRF

Enrolled patients, whose surgery is unexpectedly delayed more than 90 days after the preoperative visit, may be asked to give informed consent again.

At the end of the study period each center will provide an "End of Study Reporting Form" (see Appendix 17) to report the number of patients meeting the inclusion criteria during the study period and the total number of screening failure patients. Furthermore, each center will provide a 'Screening Failure Tracking Form' (Appendix 6) giving the reasons for screening failures at the end of the study period. Using this form, it will be possible to analyse what are the reasons for exclusion from study (e.g. subject refused to sign informed consent, subject language, cognitive difficulties, etc.).

#### 6.5 Assessment of safety and reporting

The only study-related procedure in MOPED is the follow up call at 30 days (10 minutes) and for those in hospital on Day 1 postoperatively, the QoR-15 questionnaire (3-5 min). As such, the potential for serious events appears too remote to require their definition, assessment, or documentation.

##### 6.5.1 Definition of Serious Adverse Events (SAEs)

SAEs are not applicable, because this is an observational study and no interventions are performed.

##### 6.5.2 Assessment and Documentation of SAEs

The assessment and documentation of SAEs is not required, because this is an observational study and no interventions are performed.

##### 6.5.3 Reporting of SAEs, Safety and Protective Measures

Not applicable.

## 7. STATISTICAL METHODOLOGY

### 7.1 Sample size estimation

It is proposed to evaluate a pragmatic sample of 5,000 European diabetic patients across at least 50 centres in a minimum of 15 nations. It is expected that this should be sufficient for the main epidemiological aspects of this study. It is envisaged that this target number would be enrolled over a two-year period from initial roll-out, with up to a further 12 months needed for final data acquisition, data cleaning and analysis. A sample size of 5,000 should be sufficient to avoid over-fitting and variance inflation for 50 to 70 factors and interactions based on the conventional square root or 100 values per variable respectively. In addition, a sample size of 5,000 will have at least 90% power to find a small standardized difference of

0.15 as significant at  $P < 0.05$  (Bonferroni corrected at  $P < 0.0007$ ) for up to 70 independent hypotheses and in comparing subsets of interest.

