Statistical Considerations	
Up to 5% of the population of Europe is thought to have diabetes. About 30m surgeries are performed in Europe per annum, therefore perhaps 1.5m diabetics have surgery in Europe per annum. It is proposed to evaluate a pragmatic sample of 5,000 European diabetic patients across at least 50 centres in a minimum of 10 nations.
 
Centres undertaking surgery for diabetic patients will be invited to contribute patients. It is envisaged that this target number would be enrolled over a two-year period from initial roll-out, with up to a further 12 months needed for final data acquisition, cleaning and analysis.
 
A sample size of 5,000 should be sufficient to avoid over-fitting and variance inflation for up to 63 factors or interactions. In addition, a sample size of 5,000 will have 90% power to find a small standardised difference of 0.10 as significant at <math>P < 0.05</math> for up to 63 independent hypotheses in comparing subsets of interest.

Risk-Benefit analysis	
There is no risk to patients participating in this study other than any risk associated with their perioperative care. Individual patients will not benefit from the study, but the knowledge gained from the overall evaluation will inform best practice in this previously under-researched field.

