## 7.3 Planned analyses

### 7.3.1 Main analysis

The aim of this research is to describe and quantify the epidemiology of the perioperative management of diabetic patients in Europe. Descriptive statistics such as mean (SD), median [interquartiles, range] and frequencies (%) will be presented as appropriate. The precision of the estimates will be reported with 95% confidence intervals to show the prevalence and incidence rates of diabetic phenotypes and major adverse events and complications.

The primary outcome measure is Days at Home at 30 Days (DAH-30).

Secondary outcomes include: Comprehensive Complications Index (CCI) score, based on Clavien-Dindo scale and the QoR-15 instrument measuring quality of recovery, taken only in patients who remain in hospital for Day 1 postoperative.

Secondary outcomes also include 30-day mortality, length of hospital stay, incidences of specific major adverse events (MI, MINS, AKI, PPC, CVA, PE, DVT and surgical site infection (SSI).)

Univariate analyses will be used to help identify variables of potential interest for multivariable analyses, in addition to stepwise selections. Robust multivariable regressions using maximum likelihood estimation (MLE), including Poisson and negative binomial, will be used to identify significant associations. Specific factors, or subsets of interest, will be investigated further using linear mixed models with MLE. Binary and categorical outcomes, such as occurrence of a postoperative pulmonary complication (PPC) will be analysed using multivariable logistic regression, survival analysis and Cox proportional hazards regression as appropriate.

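### The 50–70 factor capacity claimed for 5,000 patients counts patients rather than events, so it should not extend to low-incidence binary or time-to-event endpoints

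*Protocol*

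**What the plan says.** Section 7.1 sets the target: "It is proposed to evaluate a pragmatic sample of 5,000 European diabetic patients across at least 50 centres in a minimum of 15 nations". It then gives the modelling capacity: "A sample size of 5,000 should be sufficient to avoid over-fitting and variance inflation for 50 to 70 factors and interactions". The same sentence goes on to name the two rules that it relies on: "based on the conventional square root or 100 values per variable respectively". The Synopsis, under Statistical Considerations, has a different number: "A sample size of 5,000 should be sufficient to avoid over-fitting and variance inflation for up to 63 factors or interactions". Neither place says which outcomes or models the capacity refers to.

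Section 7.3.1 covers outcomes of both kinds. The primary one is a count of days: "The primary outcome measure is Days at Home at 30 Days (DAH-30"). The secondary list includes many that are binary: "Secondary outcomes also include 30-day mortality, length of hospital stay, incidences of specific major adverse events (MI, MINS, AKI, PPC, CVA, PE, DVT"). Wound infection at the operated site closes that list. For these the plan is: "Binary and categorical outcomes, such as occurrence of a postoperative pulmonary complication (PPC) will be analysed using multivariable logistic regression", with survival analysis and Cox regression as further options. Variables enter as follows: "Univariate analyses will be used to help identify variables of potential interest for multivariable analyses, in addition to stepwise selections".

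Section 7.3.3 allows exact or Firth-penalised logistic regression for sparse data where practicable. It sets no limit on the number of factors. No section gives an expected event rate or event count for any endpoint.

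**The concern.** In a linear or count model of an outcome that every patient contributes to, the number of patients is a reasonable first guide to how many terms the data can carry. In a logistic or Cox model the information comes mainly from the events. Five thousand patients with 50 deaths carry far less information about risk factors for death than 5,000 measured values of days at home.

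The capacity sentence is unrestricted, so a reader may apply it to the mortality, myocardial infarction or pulmonary embolism models as readily as to the primary outcome. If those models were built near the stated capacity, coefficients would be unstable and the selected factors would be hard to reproduce. Screening and stepwise selection would add to this, because the candidates examined use up information as well as the terms finally kept.

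**Working it through.** **Inputs from the protocol.** N = 5,000; claimed capacity 50 to 70 (7.1) or 63 (Synopsis); rules: square root of N, and 100 values per variable (7.1).

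**Assumed inputs.** Incidence, because the protocol gives none: 0.5% to 20%. Events needed per candidate parameter: 10 as the working benchmark, with 5 and 20 as the range. Each factor is counted as one parameter. This favours the plan, since a three-level factor such as the HbA1c strata uses two.

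**1. The protocol's own figure.**
- Square root of 5,000 = 70.7, about 70.
- 5,000 / 100 = 50.

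The range 50 to 70 reproduces. The order is reversed, however: as printed, the first rule (square root) is matched to 50 and the second (100 per variable) to 70. Neither rule gives the Synopsis figure of 63: 63² = 3,969, and 5,000 / 63 = 79.4 patients per factor.

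**2. Events that the claimed capacity needs.** Events = events per parameter × factors; incidence = events / 5,000.

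| Events per parameter | 50 factors | 70 factors |
|---|---|---|
| 5 | 250 (5%) | 350 (7%) |
| 10 | 500 (10%) | 700 (14%) |
| 20 | 1,000 (20%) | 1,400 (28%) |

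**3. What a given incidence supports.** Events = 5,000 × incidence; parameters supported = events / benchmark.

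| Assumed incidence | Events | Events per factor, 50 factors | Events per factor, 70 factors | Parameters at 5 per parameter | At 10 | At 20 |
|---|---|---|---|---|---|---|
| 0.5% | 25 | 0.5 | 0.4 | 5 | 2.5 | 1.25 |
| 1% | 50 | 1.0 | 0.7 | 10 | 5 | 2.5 |
| 2% | 100 | 2.0 | 1.4 | 20 | 10 | 5 |
| 5% | 250 | 5.0 | 3.6 | 50 | 25 | 12.5 |
| 10% | 500 | 10.0 | 7.1 | 100 | 50 | 25 |
| 14% | 700 | 14.0 | 10.0 | 140 | 70 | 35 |
| 20% | 1,000 | 20.0 | 14.3 | 200 | 100 | 50 |

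**4. Cross-check by a different criterion.** For a logistic model with k parameters and target shrinkage S, the minimum N is k / [(S − 1) × ln(1 − R²/S)]. Assume S = 0.9 and a Cox-Snell R² equal to 15% of its maximum, where the maximum at incidence r is 1 − exp{2[r ln r + (1 − r) ln(1 − r)]}.

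At r = 1% the maximum is 0.106 and R² = 0.0159. The minimum N is then 28,063 for 50 factors and 39,288 for 70. The corresponding pairs are:
- 10% incidence: 6,023 and 8,432
- 15% incidence: 5,004 and 7,005
- 20% incidence: 4,490 and 6,285
- 30% incidence: 3,999 and 5,598

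On this stricter criterion 5,000 patients support 50 factors from an incidence of about 15%, and still do not support 70 at 30%. It points the same way as step 3, but it depends on the assumed R².

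**The case against.** Much of the case for the protocol stands. The figures 50 and 70 are correctly computed, so there is no arithmetic slip in the range. The capacity is a ceiling: 7.1 tells nobody to put 50 to 70 terms in a mortality model, and 7.3.1 fixes no number of terms. A reader might infer that the rare-outcome models will be badly over-fitted if the plan is followed, but the text does not commit the analysts to that. Ten events per parameter is itself a rule of thumb, which is why the range 5 to 20 is shown.

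A reader might also infer that the claim is wrong for every binary endpoint. The documents do not support this. No event rates are given, and an endpoint at or above about 10% to 14% would meet the 10-per-parameter benchmark. Postoperative pulmonary complications, kidney injury, myocardial injury or wound infection could fall on either side. Nor is the claim faulted for days at home, the complications index, QoR-15 or length of stay.

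One might go further and cap centre-level and nation-level factors at 50 centres and 10 or 15 nations. Those numbers are stated minimums, not totals, and that is a separate question.

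Section 7.3.3 does provide Firth penalisation. It reduces sparse-data bias and copes with separation, which softens the consequence. It does not let 25 to 100 events support 50 to 70 coefficients.

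Finally, detailed model specification per endpoint may properly sit in a statistical analysis plan that is not shown, and its absence here is no fault. The point concerns an affirmative statement printed in the sample-size section and the Synopsis, which is broader than its basis.

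**Conclusion.** The point holds in limited form. The capacity statement rests on patient counts and names no outcome type, yet the same protocol plans logistic or Cox models for binary endpoints. Below 5% incidence the claimed 50 to 70 factors fail at 5, 10 and 20 events per parameter alike. From 5% to 28% the answer depends on the benchmark and the number of factors, and at the working benchmark of 10 the threshold is 10% to 14%.

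That any named endpoint lies below these thresholds is an assumption, because the protocol gives no rates. The primary outcome and the descriptive incidence estimates are unaffected, and nothing here shows that 5,000 patients are too few for the study's main aim. It is a statement that should be corrected, bearing on the secondary binary endpoints. The mismatch between 63 and 50 to 70, and the reversed order of the two rules, are small errors in the same claim.

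**What to change.** In 7.1 and in the Synopsis:
- Say that the factor capacity applies to models of non-binary outcomes only.
- Use the same figure in both places, one that the stated rules give: 50 by 100 patients per variable, 70 by the square root, with the rules listed in that order.
- Add that for each binary or time-to-event endpoint the number of candidate parameters, including those screened and dropped, will be limited by the observed number of events, for example to about one tenth of it.

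Possible wording for the addition: *For binary and time-to-event outcomes, model size will be governed by the number of observed events and not by the number of patients; the number of candidate parameters will not exceed about one per ten events.*

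The Firth provision in 7.3.3 can stay as it is. The cost is a few sentences, with no additional patients or data. The downside is that models for rare outcomes become smaller, so fewer potential risk factors can be examined for those endpoints.

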### 3. OBJECTIVES, ENDPOINTS/OUTCOMES AND OTHER STUDY VARIABLES

#### 3.1 Objectives

1. To document, in a large scale observational, epidemiological study, the perioperative glycaemic management of established diabetic patients undergoing every type of surgery with anaesthesia in Europe.
2. To document the type, incidence and severity of all postoperative complications occurring up to 30 days postoperatively.
3. To document the impact of all complications by determining the number of days at home at 30 days (DAH-30, primary outcome), Comprehensive Complications Index (CCI) score, based on the Clavien-Dindo scale and other secondary outcomes.
4. To undertake sub-group analysis comparing these outcomes among:
  - DM1, DM2 and Other Diabetes ('Other' includes Maturity Onset Diabetes of the Young, (MODY) and LADA and any other type of diabetes).
  - Patients with different strata of pre-operative glycaemic control, i.e. HbA1c <53, HbA1c 53-69 and HbA1c >69 mmol. mmol;[11]
  - Patients who received different anaesthetic techniques:
    - Volatile versus total intravenous anaesthesia.
    - Regional versus general anaesthesia (GA) and
    - Patients receiving combined GA and regional anaesthesia versus GA alone.

A list of the a priori hypotheses is listed in Appendix 9.

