### 7.3.4 Ancillary analyses

In addition to the sensitivity analyses as described, the effects of pre-defined subsets will be investigated. These subsets will include: DM1, DM2, DM3, MODY and LADA diabetic patients; Strata of glycaemic control, HbA1c <53, HbA1c 53-69 and HbA1c >69 mmol/mmol;

Anaesthetic techniques, inhalational (IA) versus total intravenous (TIVA), regional (RA) versus general (GA), combined GA and RA versus GA alone.

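### Section 7.1 claims 90% power for subset comparisons without a size limit; it cannot hold for every pair of a three-level subset, or for a subset below about 26% compared with the rest

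*Protocol*

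**What the plan says.** Section 7.1 states that "a sample size of 5,000 will have at least 90% power to find a small standardized difference of" 0.15 ("Bonferroni corrected at" P < 0.0007), and that this applies "for up to 70 independent hypotheses and in comparing subsets of interest". It gives no group split, no subset size, no sidedness and no allowance for clustering.

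The subsets are named elsewhere. Section 3.1 lists "Patients with different strata of pre-operative glycaemic control" (HbA1c <53, 53-69 and >69), "DM1, DM2 and Other Diabetes", and three contrasts of anaesthetic technique. The synopsis makes subgroup outcomes, particularly by HbA1c stratum, a main objective. Section 7.3.4 repeats the HbA1c strata and the anaesthetic contrasts but divides diabetes type differently: "These subsets will include: DM1, DM2, DM3, MODY and LADA diabetic patients". That is five groups where 3.1 has three. Section 3.1 places MODY and LADA inside Other; DM3 is not defined or used anywhere else in the protocol.

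**The concern.** The power of a two-group comparison depends on the sizes of the two groups compared, not on the total enrolled. A figure that is correct for two halves of 5,000 does not carry over to strata that are smaller or number more than two. Section 7.1 extends it to subsets without saying so.

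The stratum comparison by HbA1c is a headline aim. A reader who trusts 7.1 could take a non-significant difference between two strata as a negative result obtained with 90% power, when the design may give clearly less. The mismatched diabetes-type lists add to this, because the number and size of the groups to be compared are not fixed.

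**Working it through.** **Inputs.** From 7.1: N = 5,000, standardised difference d = 0.15, power 90%, per-test P < 0.0007 (0.05/70 = 0.000714). Assumed, because 7.1 is silent: two-sided test, normal approximation, independent patients.

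**Formula.** With h = n1·n2/(n1+n2), power = Φ(d·√h − z), where z = 3.390 for two-sided 0.0007. The normal quantile for 90% power is 1.282.

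**Reproducing the stated figure.** For 2,500 v 2,500, h = 1,250 and power = Φ(0.15 × 35.36 − 3.390) = Φ(1.914) = 97%. So "at least 90% power" is correct for a balanced split of the whole cohort.

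**Size condition for 90%.** h ≥ ((3.390 + 1.282)/0.15)² ≈ 970.
- Equal groups: h = n/2, so n ≈ 1,940 per group (3,880 in total).
- One subset v all the rest of 5,000: 5,000·p(1−p) ≥ 970, so p ≥ 0.5 − √(0.25 − 0.194) ≈ 0.26.

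**Three levels, all pairs.** The two smallest groups together hold at most two thirds of 5,000, or 3,333. Since h is at most (n1+n2)/4, the weakest pair has h ≤ 833, which is below 970 whatever the split. To reach 970 the two smallest groups need 3,880 patients between them, and the third group must be at least 1,940, so the total is at least 5,820. With equal thirds, power per pair = Φ(0.15 × 28.87 − 3.390) = Φ(0.941) = 83%. This needs no assumption about stratum shares.

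**Other contrasts at P < 0.0007:**

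| Contrast | h | Power at 0.15 |
|---|---|---|
| 2,000 v 2,000 | 1,000 | 91% |
| One third v the other two thirds | 1,111 | 95% |
| 2,000 v 1,000 | 667 | 69% |
| 20% v the rest | 800 | 80% |
| 10% v the rest | 450 | 42% |
| 5% v the rest | 237.5 | 14% |

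The protocol gives no subset shares; the 20%, 10% and 5% are illustrations.

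**Detectable difference at 90% power** = (3.390 + 1.282)/√h: 0.162 for a pair of equal thirds; 0.165, 0.22 and 0.30 for a 20%, 10% or 5% subset v the rest.

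**Sensitivity.** Using 0.05/70 unrounded gives 1,935 per group and 3 × 1,935 = 5,805 for three levels. A one-sided test at 0.0007 still needs 3 × 1,782 = 5,346. Neither fits within 5,000.

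**The case against.** The strongest reply is that the printed figure reproduces, and that 7.1 presents the sample as pragmatic, with a mainly descriptive aim in 7.3.1. The protocol does not say that HbA1c or diabetes type will be tested pair by pair; it plans regression and mixed models. The list of a priori hypotheses is in Appendix 9, which is not at hand, so the contrasts that make up the 70 are unknown. A 2-df overall test in equal thirds has about 90% power if one group differs from the other two by 0.15, though only 74% if the three means are evenly spaced over 0.15. At an uncorrected 0.05, equal thirds would give 99% per pair.

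Much of this stands, and it rules out several stronger readings:
- A reader might infer that 90% power is wrong throughout, or impossible for any analysis of a three-level factor. It is not: one large pair, one level v the rest, or one omnibus pattern can reach 90%.
- A reader might infer that all 5,000 must be split into two groups. They need not be: 2,000 v 2,000 is enough, so a contrast that uses only part of the cohort does not fail for that reason.
- A reader might infer that 7.1 promises power for comparing centres or nations. The synopsis asks whether practice varies between them, but 7.3.4 does not list them as subsets, and any clustered power figure would rest on an assumed intraclass correlation.
- The 7.3.4 diabetes list can be read as Other broken into its parts, but DM3 still has no definition.

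What does not stand is the unqualified extension to subsets. The sentence in 7.1 names the corrected threshold and attaches subset comparisons to it, so the uncorrected 0.05 is not a available reading of it. A later analysis plan cannot supply the missing patients.

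**Conclusion.** The concern holds in a limited form. The claim in 7.1 is true for balanced halves (97%) and for other contrasts with h of about 970 or more. As an unconditional statement about subset comparisons it is not true. For all pairs of a three-level subset at the corrected threshold it is unattainable: about 5,820 patients are needed against 5,000, and 83% per pair is the best case. This rests only on the protocol's own figures, a two-sided normal approximation and independent patients, and a one-sided test does not change the conclusion. For one subset v the rest, the threshold of about 26% is equally firm, but how far any actual subset falls below it depends on shares that the protocol does not give. Section 7.3.2 nests patients within centre, and the figures here make no allowance for that.

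The two diabetes-type lists also disagree and need reconciling, whatever view is taken of power.

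**What to change.** In 7.1, claim 90% power at 0.15 and P < 0.0007 only for two-group contrasts with n1·n2/(n1+n2) of at least about 970, and translate this for the reader: about 1,940 per group when equal, or at least about 26% of 5,000 when one subset is compared with the rest. For other contrasts give the difference detectable with 90% power: 0.162 for a pair of equal thirds, and 0.165, 0.22 and 0.30 for a 20%, 10% or 5% subset v the rest, marked as illustrative shares. Add that all these figures assume no clustering by centre.

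Use one diabetes-type grouping in 3.1 and 7.3.4, and either define DM3 or remove it.

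The cost is a few sentences in 7.1 and one in 7.3.4. The stated power becomes less favourable; sample size, data collection and analysis method stay as they are.
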